3 OVERALL STUDY DESIGN

The study is a phase Phase III, randomized, penta-blind, placebo-controlled, multicenter trial with a non-inferiority design. The trial will be conducted and reported according to the CONSORT statement (Consolidated Standards of Reporting Trials), the SPIRIT initiative (Standard Protocol Items: Recommendations for Interventional Trials), and Good Clinical Practice (GCP) standards, and registered in ClinicalTrials.gov

Study Period	Estimated date of first patient enrolled: 01.10.15 (startup at Sørlandet Hospital 2015, recruitment from other centres gradually during 2016)
	Anticipated recruitment period: 01.10.15 - 31.12.19
	Estimated date of last patient completed: 31.12.20
Treatment Duration:	Six weeks
Follow-up:	13 months

4 STUDY POPULATION

4.1 Selection of Study Population

The study will be headed from Sørlandet Hospital HF (SSH). Selected hospitals throughout Norway (5-10) will recruit consecutive patients diagnosed with LNB. A contact person, familiar with diagnosis and treatment of LNB, at each study site will be trained in the current study and in general GCP.

4.2 Number of Patients

We plan to enroll 120 patients, 60 in each treatment arm.

4.3 Inclusion Criteria

In everyday clinical practice, patients with suspected LNB are routinely examined neurologically and their CSF is analyzed regarding cell count, protein level, IgG index, oligoclonal bands (OCB's) and *Bb* antibodies (including

calculations whether there are intrathecal production of *Bb* antibodies). Diagnostics may be somewhat uncertain in subacute cases as antibiotic treatment is often initiated before *Bb* antibody results are available, and *Bb* antibody production may be absent in early phases of LNB. In this trial, we will therefore use the following inclusion criteria:

1. Neurological symptoms suggestive of LNB without other obvious reasons, and one or both of

- a. CSF pleocytosis (leucocytes $\geq 5/\text{mm}^3$)**
- b. Intrathecal *Bb* antibody production**

2. Signed informed consent

During the course of the disease, the patients will be classified as either definite or possible LNB according to European diagnostic criteria (Table 4) (1).

Table 4. European diagnostic criteria

**If criterion 3 is lacking after a duration of six weeks, there have to be found *Bb*-specific antibodies in serum.*

Definite LNB	Possible LNB ^a
All three criteria fulfilled	Two criteria fulfilled
1. Neurological symptoms suggestive of LNB without other obvious reasons 2. Cerebrospinal fluid pleocytosis 3. Intrathecal Bb antibody production	

4.4 Exclusion Criteria

Patients will be excluded from the study if they meet any of the following criteria:

- Age less than 18 years**
- Pregnancy, breast-feeding and/or women of childbearing potential not using adequate contraception.** Adequate contraception include oral, injected or implanted hormonal methods of contraception, placement of an intrauterine device or system, vasectomized partner, or sexual abstinence imposed during treatment.
- Adverse reaction to tetracyclines**
- Treatment with cephalosporin, penicillin, or tetracycline macrolide during the last 14 days before start of doxycycline treatment ***
- Serious liver or kidney disease that contraindicates use of doxycycline**
- Lactose intolerance**
- Need to use medications contraindicated according to SmPC of the IMP (Antacid drugs, Didanosin, Probenecide, Phenobarbital, Phenytoin, Carbamazepine, Rifamphicin)**

*If used for other conditions than LNB, or if the active LNB has been treated with antibiotic drugs or dosage deviating from the protocol

5 TREATMENT

For this study, doxycycline and placebo are defined as Investigational Medicinal Product (IMP).

Included patients will be randomized to two weeks treatment with oral doxycycline (200 mg once daily) followed by four weeks placebo or six weeks treatment with oral doxycycline (200 mg once daily).

5.1 Drug Identity, Supply and Storage

IMPs (active drug and placebo) will be produced at Kragerø Tabletproduksjon. Production documentation is described in a separate document (Appendix B). All included patients will receive active drug (doxycycline) for 14 days, thereafter half of them will receive placebo and the other half will receive active drug (doxycycline) for four weeks.

5.2 Dosage and Drug Administration

Both active drug and placebo will be administered per os as capsules every 24 hours. IMPs should be taken together with abundant water and a small meal. Iron tablets, calcium preparations yoghurt, milk and food/ beverages that contain calcium may weaken the effect of doxycycline, and should not be taken less than three hours before or after intake of IMP.

5.3 Duration of Therapy

The patients will be treated for six weeks unless disease progression (see section 8.3) or unacceptable toxicity.

5.4 Concomitant Medication

The following medications are not allowed while the patient is in the treatment phase of the study:

- Antacid drugs (single use)
- Didanosin (single use)
- Probencide (chronic use)
- Phenobarbital (chronic use)
- Phenytoin (chronic use)
- Carbamazepine (chronic use)
- Rifampicin (chronic use)

All concomitant medication (incl. vitamins, herbal preparation and other “over-the-counter” drugs) used by the patient will be recorded in the patient’s file and CRF.

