2.1 Primary Endpoint

The primary endpoint is improvement on a composite clinical score (Table 2) from inclusion to six months after ended treatment defined as clinical score at inclusion minus clinical score at six months.

Subjective symptoms	
Subjective symptoms related* by the patient to the current/recent LNB	Score
Malaise (sykdomsfølelse, redusert almentilstand)	
Fatigue (trøtthet, utmattelse)	
Headache (hodepine)	
Neck and/or back pain (nakke og/eller ryggsmerte)	
Abdominal and/or breast pain (smerter i bryst og/eller mageregion)	
Arm pain (smerter i armer)	
Leg pain (smerter i ben)	
Generalized pain located to joints and/or muscles (smerter i "hele kroppen" (ledd og muskler))	
Memory and/or concentration problems (hukommelse og/eller koncentrasjonsproblemer)	
Other (annet)	
Objective findings, PNS	
Findings related* to the current/recent LNB	Score
Facial palsy (facialisparese)	
Paresis of eye muscles (øyemuskelparese)	
Reduced hearing (redusert hørsel)	
Other cranial neuropathies (andre hjernenerveutfall)	
Cervical radicular sensory findings ^a (cervikale radikulære sensoriske funn)	
Cervical radicular paresis ^b (cervikal radikulær parese)	
Thoracal radicular sensory findings ^a (thoracale radikulære sensoriske funn)	
Lumbar radicular sensory findings ^a (lumbale radikulære sensoriske funn)	
Lumbar radicular paresis ^b (lumbal radikulær parese)	
Non-radicular sensory findings ^c (ikke-radikulære sensoriske funn)	
Non-radicular paresis ^d (ikke-radikulær nevropati med pareser)	
Other (annet)	
Objective findings, CNS	
Findings related* to the current/recent LNB	Score
Central findings ^e in one extremity (sentralnervøse funn i en ekstremitet)	
Central findings ^e in a hemi pattern (sentralnervøse funn i en kroppshalvdel)	
Central findings ^e in both legs (sentralnervøse funn i begge ben)	
Central findings ^e in all extremities (sentralnervøse funn i alle ekstremiteter)	
Gait ataxia (gangataksi, ustøhet)	
Dysphasi/aphasi (talevansker)	
Nystagmus (nystagmus)	
Involuntary movements including tremor (ufrivillige bevegelser inkl. skjelving)	
Cognitive impairment (kognitiv svikt/forvirring)	
Other (annet)	
Total score	

Table 2. Composite clinical score.

Each item is scored 0=none, 1=mild, without influence on daily life, or 2=severe, with influence on daily life.

Maximum total score=64 (sum of subjective symptoms and objective findings)

* Temporally and otherwise related to current LNB

^a Abnormal sensory findings in a radicular pattern

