6.2.5 Six months After End of Treatment (Follow-up)

- Interview about symptom description, concomitant medication, and sick leave attributable to LNB
- Composite clinical score
- FSS, PHQ-15, SF-36
- Laboratory analyses
 - Blood: Hb, white blood cell count with differential, platelet count, ASAT, ALAT, GT, ALP, Creatinine, CRP, electrophoresis, Bb antibodies, TBE antibodies
 - CSF: Cellcount, protein level, Oligoclonal bands, Bb antibodies,
 - In addition aliquots of specimens will be transferred for biobank storage
- Cerebral MRI and neuropsychological testing in a subset of patients (Appendix A)

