6.4 Procedures for Discontinuation

6.4.1 Patient Discontinuation

Patients who withdraw or are withdrawn from the study, will either stop further treatment or receive another antibiotic therapy. If possible, a final assessment shall be made (withdrawal visit and/or follow-up visits). The reason for discontinuation will be recorded, and the investigator will follow up any significant adverse events until the outcome is either recovered or resolved. Patients who withdraw or are withdrawn from the study before start of treatment, will be replaced.

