10.5 Statistical Analysis **[name]?

Results will be reported as mean scores with standard deviation or proportions as appropriate.

To compare the two groups on the primary outcome, we will use a general linear model with treatment group was factor and adjust for duration of symptoms, gender and age. The analysis will be conducted according to the intention to treat principle.

For other analysis, comparison between groups will be done with e.g. independent samples t-test, nonparametric Mann-Whitney-U test or Pearsons chi-square test for crosstabs as appropriate.

P-values <0.05 are considered statistically significant.

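### Non-study antibiotics taken after randomisation are recorded, but neither the endpoint, the per-protocol set nor the analysis says how they are handled; if two weeks is truly worse and retreatment works, the intention-to-treat comparison will understate the deficit

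*Combined protocol and SAP*

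**What the plan says.** Section 5.1 gives every patient active drug for 14 days, then four weeks of active drug or placebo. The randomised contrast is therefore antibiotic exposure in weeks 3 to 6.

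At entry, section 4.4 excludes "Treatment with cephalosporin, penicillin, or tetracycline macrolide during the last 14 days before start of doxycycline treatment". I read this as four classes; the synopsis names three, without macrolides. A footnote limits the exclusion to use for another condition, or to treatment of the current LNB that departs from the protocol. Under section 5.6, patients already taking doxycycline 200 mg daily may enter.

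After entry, section 5.4 states: "The following medications are not allowed while the patient is in the treatment phase of the study". Seven drugs follow (antacids, didanosine, probenecid, three anticonvulsants and rifampicin). None belongs to the classes in section 4.4, and no list applies in follow-up.

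Section 6.4.1 adds: "Patients who withdraw or are withdrawn from the study, will either stop further treatment or receive another antibiotic therapy". It also asks that such patients be assessed at withdrawal or follow-up visits where possible.

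Concomitant medication goes into the CRF (5.4). It is registered weekly to week 10 (6.1) and asked about again at six months: "Interview about symptom description, concomitant medication, and sick leave attributable to LNB".

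The primary endpoint is "defined as clinical score at inclusion minus clinical score at six months" (2.1), with no condition on antibiotics taken in between. Section 10.5 says: "The analysis will be conducted according to the intention to treat principle". Section 10.3 defines a per-protocol set by the absence of significant deviations, without defining these. Section 10.5 gives that set no role in the primary comparison.

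**The concern.** Take a two-week patient who finishes the capsules, still has complaints at week 10, and is given another antibiotic before month 6. The plan scores this patient at six months as a two-week result, and nothing marks the score as different. A withdrawn patient who receives another antibiotic and attends follow-up is also scored under the arm assigned.

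In a superiority trial, dilution of this kind is usually conservative. In a non-inferiority trial it works in favour of the claim. The stated question is whether two weeks does as well as six. If enough two-week patients are retreated, the comparison answers another question: whether two weeks, with retreatment as needed, does as well. Section 1.1 also intends the arm contrast to address the persistent-infection hypothesis, and the same dilution would weaken that inference.

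**Working it through.** **The plan's own figure.** The planned 120 patients (60 per arm, section 4.2) cannot be reproduced, because no margin, power or sidedness is stated. The margin that 60 per arm would imply can be found instead.

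**Inputs from the documents**
- SD 2.6 and mean 1.7 (section 10.1). These describe a 12-month score on a slightly different scale, not six-month improvement.
- 60 patients per arm (4.2).
- 25–50% of patients with residual complaints (1.1).

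**Assumptions.** One-sided 0.025; 80% power; true difference zero for sizing. The retreatment share and its effect are not in the documents and are varied.

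**Step 1: standard error and implied margin**
- SE = 2.6 × √(2/60) = 0.475.
- Margin at 80% power = (1.96 + 0.84) × 0.475 = 1.33. At 90% power it is 1.54.

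**Step 2: how many patients could be involved**
- Residual complaints: 60 × 0.25 = 15 to 60 × 0.50 = 30 per arm.
- If 10–50% of these are retreated (assumed): 15 × 0.10 = 1.5 to 30 × 0.50 = 15 per arm.

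**Step 3: false non-inferiority.** Let two weeks be truly worse by exactly the margin M, and let retreatment remove a share f of that deficit. Then P(false non-inferiority) = Φ(f × M / SE − 1.96). For M = 1.33 and f = 0.25: 0.25 × 1.33 / 0.475 = 0.70, and Φ(0.70 − 1.96) = 10.4%.

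| Assumed margin | f = 0 | f = 10% | f = 25% | f = 50% |
|---|---|---|---|---|
| 1.00 | 2.5% | 4.0% | 7.6% | 18.2% |
| 1.33 | 2.5% | 4.6% | 10.4% | 28.8% |
| 1.54 | 2.5% | 5.1% | 12.5% | 36.8% |

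**Step 4: does the mechanism survive blinding?** I simulated 20,000 trials with negative-binomial scores (mean 1.7 and SD 2.6 in the six-week arm). The true deficit was 1.33. The same blinded rule applied in both arms: a patient scoring 2 or more may be retreated.

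| Share of symptomatic patients retreated, and effect | Observed deficit | Points hidden | False non-inferiority |
|---|---|---|---|
| none | 1.33 | 0 | 3.0% |
| 20%, score halved | 1.20 | 0.13 | 5.3% |
| 30%, score halved | 1.13 | 0.20 | 7.1% |
| 50%, score halved | 1.00 | 0.33 | 13.7% |
| 50%, fully relieved | 0.67 | 0.66 | 35.9% |

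In the two 50% rows, about 28% of two-week and 18% of six-week patients are retreated, although nobody knows the arm. With no true difference, the estimated difference stays at 0 under every rule.

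**The case against.** The strongest reply is that intention to treat already settles the matter: every score counts, whatever happened in between. That is a legitimate treatment-policy choice, and it should remain primary. What it leaves open is whether that choice was meant for non-study antibiotics, which no section says.

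A reader might infer that the plan is biased toward non-inferiority as it stands. The documents do not support that. Section 10.2.2 blinds patients and investigators until all six-month visits are complete, so retreatment cannot follow the arm. If retreatment is equally common in both arms and removes the same number of points per patient, the difference does not move. Bias requires two weeks to be truly worse and retreatment to work. Section 1.2 gives mixed evidence on longer treatment: a controlled study of 152 patients found similar outcomes with prolonged antibiotic and placebo, while an open-label comparison found more failures with 14 than with 28 days. The reply to this is narrower: non-inferiority error matters only when two weeks is worse, and if longer exposure helps, later antibiotic may well help too.

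A reader might also infer that antibiotic use goes unnoticed. It does not. It is recorded; chronic rifampicin is barred during treatment; and worsening attributed to LNB despite 14 days of doxycycline is disease progression (8.3) and a reason for discontinuation (6.3), with the reason documented (6.4.1). The list in 5.4 repeats the SmPC-based list in 4.4 and was evidently not written to control antibiotic exposure. All of this stands, but none of it says how the resulting scores are analysed.

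**Conclusion.** The gap is real and the bias is conditional. Non-study antibiotics bear directly on the only thing that differs between the arms, and the plan collects them without saying what they mean for the endpoint, the per-protocol set or the conclusion. If two weeks is truly worse and retreatment works, the observed deficit shrinks even under full blinding. If the arms are equal, the estimate is unbiased.

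The size cannot be fixed from the documents, because the margin, the retreatment frequency and its effect are all absent. With an assumed margin of 1.33, modest retreatment (20–30% of symptomatic patients, scores halved) hides 0.13 to 0.20 points and raises false non-inferiority to about 5–7%. Heavy, fully effective retreatment hides about 0.66 points and raises it to about 36%. Claims toward the upper end need assumptions that nothing in the documents supports. The figures also take the earlier trial's 12-month SD as a stand-in for the SD of six-month improvement.

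**What to change.** Keep the intention-to-treat analysis as primary. Before database lock and unblinding (section 10.4 allows amendment until lock):

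1. Add an indication field (LNB complaints or other infection) for any non-study antibiotic from the classes in 4.4 taken between randomisation and the six-month visit. Tabulate use, timing and indication by arm.
2. Class use for LNB complaints as a significant protocol deviation for the per-protocol set, and report the per-protocol comparison of the primary endpoint beside intention to treat. This set cannot carry the point alone: dropping retreated patients removes poor responders, possibly more of them from the worse arm.
3. Pre-specify one supplementary primary analysis under a single rule, applied alike in both arms. One example is improvement set to zero for patients retreated for LNB complaints. Carrying forward the last score before retreatment is a different analysis and should not be mixed with it. The zero rule is deliberately severe, since section 1.1 notes that recovery can take up to a few months.
4. Interpret a non-inferiority conclusion in light of whether these analyses are consistent with intention to treat against the same margin, which must first be stated. This guides interpretation and is not an automatic veto.

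Sections 4.4, 5.4 and 6.4.1 should be reconciled on non-study antibiotics, including which classes are meant. No clinical rule on antibiotic use is proposed, and patient care is unchanged.

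The cost is one CRF field, some analysis-plan wording and one extra analysis. A non-inferiority claim becomes somewhat harder to make.

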5.5 Subject Compliance

Pillcount and patients compliance diary will be used to determine adherence to treatment.

5.6 Drug Accountability

The responsible site personnel will confirm receipt of study drug and will use the study drug only within the framework of this clinical study and in accordance with this protocol. Distribution and return of the study drug will be documented in the drug accountability log and in the CRFs.

If patients are included in the study after already having started doxycycline 200 mg per day, the responsible site personnel will ensure that the appropriate amount of capsules, depending on the number of days already treated, are removed from the study drug packaging before distribution to the patients. The amount of study drug delivered to the patients will be documented in the CRF.

5.7 Drug Labeling

The IMPs will have a label permanently affixed to the outside and will be labeled according with GCP and national regulations (29, 30), stating that the material is for clinical trial/investigational use only and should be kept out of reach of children. The labeling will be prepared by Kragerø Tabletproduksjon. All text will be in Norwegian. Labeling details are described in separate document attached (Appendix C).

Labels will also include blank lines for:

- Patient’s initials
- Patient’s enrolment code
- Date dispensed
- Name of prescribing doctor

5.8 Subject Numbering

Each subject is identified in the study by a unique subject number that is assigned when the subject is entered into the eCRF for the first time, after signing the Informed Consent Form. Once assigned the subject number cannot be reused for any other subject. The study treatment will be dispensed to the subject by authorized site personnel only.

6 STUDY PROCEDURES

6.1 Flow Chart

Time	Baseline	Treatment and post-treatment Period Week 1-10					Follow-up Period	
		Once weekly	Week 2 - 4	Day 6-8 after start of treatment	End of week 10	6 months after end of treatment	12 months after end of treatment	
Enrollment and Informed consent	x							
Basic demographics	x							
Medical History	x							
Concomitant medications	x					x	x	

Time	Baseline	Treatment and post-treatment Period Week 1-10					Follow-up Period	
		Once weekly	Week 2 - 4	Day 6-8 after start of treatment	End of week 10	6 months after end of treatment	12 months after end of treatment	
Telephone to check for reasons to discontinue IMP (treatment failure, toxicity, and so on)				x				
Composite clinical score (Table 2)	x				x	x	x	
FSS	x				x	x	x	
PHQ-15						x	x	
SF-36						x		
CSF sampling	X**					x	x	
Blood sampling	X**					x	x	
IMP delivery	x							
Patientregistration of compliance, concomitant medication, and adverse events (Table 3)		x						
Bloodtests to check toxicity of treatment	x		xx					
Pill count and collection of patients diaries					x			
Cerebral MRI*			x				x	
Neuropsychological screening tests*			x					
Neuropsychological testing*						x		

Table 5. Trial flow chart

*a subset of patients (WP4)

** obtained by clinican before inclusion

6.2 By Visit

Clinical data will be collected in a clinical research e-database at Department of clinical research support at Oslo University Hospital (OUS).

Informed consent

Informed consent must have been given voluntarily by each subject before any study specific procedures are initiated.

6.2.1 Screening Visit

- Evaluate patient eligibility based on symptoms, findings and CSF findings
- Demographic data: Age, sex, education, occupational status, civil status
- Medical history: Comorbidity, medication, tick bite (ever and last six months), Erythema Migrans (ever and last six months), earlier treatment for Lyme borreliosis
- Clinical picture: Symptom description, symptom duration
- Physical examination: General clinical and neurological examination including composite clinical score
- Concomitant medication: All concomitant medication (incl. vitamins, herbal preparation and other “over-the-counter” drugs) used by the subject within 28 days of treatment start will be recorded in the CRF.
- Laboratory analysis from samples obtained before inclusion
 - Blood: Hb, white blood cell count with differential, platelet count, ASAT, ALAT, GT, ALP, Creatinine, CRP, electrophoresis, *Bb* antibodies, TBE antibodies. Pregnancy test should have been taken within the last 14 days before inclusion in fertile women.
 - CSF: Cellcount, protein level, Oligoclonal bands, *Bb* antibodies, PCR for Herpes Simplex Virus (HSV), Varicella Zoster Virus (VZV) and Enterovirus
- In addition aliquots of specimens will be transferred for biobank storage after inclusion

- FSS

